#### **PATIENT EDUCATION:**

There is an educational initiative currently underway at Cleveland Clinic to improve the inpatient colonoscopy experience which will also be applicable to all the patients enrolled in our study. The initiative entails:

- 1) Educating the nurses (via educational posters and small didactic sessions),

2) Educating the internal medicine and surgery residents who order the bulk of the inpatient colonoscopies (via educational posters and small didactic sessions),

3) Educating the patients (via detailed instructional pamphlets which will be distributed on the day before the colonoscopy)

Every patient who consents for inclusion in our study will also receive written instructions educating them about the appropriate preparation that needs to be undertaken to make their colonoscopy successful, with special emphasis on proper technique of the bowel cleansing process. Additionally, an investigator or study coordinator would be available to answer any questions that the patient might have related to the bowel purgatory process or the procedure itself.

A clear liquid diet is preferred after awakening the entire day before the procedure. Patients will not be excluded from participating in the study if they have eaten solid food the day before the procedure. Patients will be instructed to consume clear liquids (no solid food) once they begun consuming the bowel preparation until after their colonoscopy. To ensure better comprehension of the patient and success of the bowel cleansing process, the written instructions will specify drinks that qualify as clear liquids. The patient's in each group will be instructed to consume the bowel preparation agent as per their approved FDA labels. Administration of bowel preparations as a split dose is currently the recommendation of choice, for colonic cleansing prior to colonoscopy, in national guidelines (including American Society of Gastrointestinal Endoscopy, American College of Gastroenterology and United States Multi-Society Task Force for colorectal cancer screening).

1) 4 LITER PEG-ELS GROUP (CONSCIOUS SEDATION/SINGLE DOSE DAY BEFORE):

Group A will be instructed to drink the 4-liter PEG-ELS at rates of 8 ounces (240 ml) every 10 min the evening before their colonoscopy and finish drinking the bowel preparation in three hours. They may continue to drink additional clear liquids until 2 hours before their colonoscopy.

2) 4 LITER PEG-ELS GROUP (CONSCIOUS SEDATION/SPLIT DOSE):

Group B will be instructed to complete their bowel preparation in two steps for split dosing regimen. They will begin drinking an 8-ounce glass of bowel preparation every 10 minutes for a total of 8 glasses (~ 2 liters) the evening before the colonoscopy and finish drinking the bowel preparation in 1.5 hours . They may continue to drink additional clear liquids. This dosing scheme will then be repeated 4 hours before the scheduled time of their colonoscopy where they will drink an 8-ounce glass of PEG-ELS every 10

minutes for a total of 8 glasses (~2 liters) and finish drinking the bowel preparation in 1.5 hours. They may continue drinking additional clear liquids until 2 hours before their colonoscopy.

3) SP/MC GROUP (CONSCIOUS SEDATION/SINGLE DOSE DAY BEFORE):

Group C will be instructed to drink sodium picosulfate, magnesium oxide and anhydrous citric acid (CLENPIQ) which is ready to drink and does not need to be diluted. Patients will consume the first bottle of SP/MC the afternoon or evening before their colonoscopy followed by at least five (5) 8-ounce glasses of clear liquids consumed at their own pace, within the next 5 hours. The patient will consume the second bottle of SP/MC 5 hours after beginning the first bottle followed by at least 3 8-ounce glasses of clear liquids within the next 2 hours.. They may continue to drink additional clear liquids until 2 hours before their colonoscopy.

4) SP/MC GROUP (CONSCIOUS SEDATION/SPLIT DOSE):

Group D will be instructed to drink sodium picosulfate, magnesium oxide and anhydrous citric acid (CLENPIQ) which is ready to drink and does not need to be diluted. . Patients will complete their bowel preparation in two steps for the split dosing regimen. Patients will consume the first bottle of SP/MC the afternoon or evening before their colonoscopy followed by at least five (5) 8-ounce glasses of clear liquids consumed at their own pace, within the next 5 hours. Patients may continue drinking additional clear liquids. This dosing scheme will then be repeated 4 hours prior to their colonoscopy. Patients will consume the second bottle of SP/MC followed by at least 3, 8 ounce glasses of clear liquids over the next two hours. . They may continue drinking additional clear liquids until 2 hours before their colonoscopy.

5) 4 LITER PEG-ELS GROUP (GENERAL ANESTHESI/SINGLE DOSE DAY BEFORE):

Group E will be instructed to drink the 4-liter PEG-ELS at rates of 8 ounces (240 ml) every 10 min the afternoon or evening before their colonoscopy and finish drinking the bowel preparation within 3 hours and no later than midnight . They may continue to drink additional clear liquids until midnight and then nothing to eat or drink until after their colonoscopy.

6) SP/MC GROUP (GENERAL ANESTHESIA/SINGLE DOSE DAY BEFORE):

Group F will be instructed to drink sodium picosulfate, magnesium oxide and anhydrous citric acid (CLENPIQ) which is ready to drink and does not need to be diluted. Patients will consume the first bottle of SP/MC **the afternoon or evening** before their colonoscopy followed by at least five (5) 8-

ounce glasses of clear liquid consumed at their own pace, within the next 5 hours. The patient will consume the second bottle of SP/MC 5 hours after beginning the first bottle followed by at least 3 glasses of 8-ounce clear liquids which must be completed by midnight the day before the procedure. They may continue to drink additional clear liquids until midnight and then nothing to eat or drink until after their colonoscopy.

### **ASSESSMENT OF PATIENT TOLERABILITY AND ADVERSE EFFECTS:**

Each patient will be provided a survey at the time of enrollment. The patients will be instructed to complete the survey in “real time” (as they are drinking the preparation). The co-investigator or the study coordinator will collect the survey from the patient prior to receiving sedation for their colonoscopy procedure. The co-investigator or study coordinator will review the survey to ensure all questions are answered.

The purpose of the survey will be to document the following information:

- a. Demographic details (including level of education and annual income),
- b. The start time and end time of the ingestion of bowel cleansing agent,
- c. Total amount of the cleansing agent ingested (to be recorded using a visual depiction of the remaining bowel preparation agent in the container),
- d. Full dose of the bowel cleanser ingested (yes versus no),
- e. Details including the type and timing of symptoms encountered (nausea, vomiting, abdominal pain, bloating, thirst, dizziness, headache or paresthesia),
- f. If any of the above-mentioned symptoms were present prior to the start of the cleansing process, did the use of the purgative agent make them worse (yes versus no),
- g. Ease of use based on a modified 5-point Likert scale: “very easy,” “easy,” “tolerable,” “difficult,” or “very difficult” (score 5–1, respectively),
- h. Palatability based on a modified 5-point Likert scale: “very good,” “good,” “fair,” “bad,” or “worst” (score 5–1, respectively), – *Patients who score ≥3 points in items h) and i) will be classified as the tolerant group.*
- i. Willingness to use the same agent again (yes versus no),

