## **INTRODUCTION & BACKGROUND:**

Effective bowel cleansing is paramount for adequate visualization of the colonic mucosa. Inadequate bowel preparation is reported in as high as 20-30 % of all outpatient procedures but it is higher in hospitalized patients with rates up to 50 % being reported. Hospitalization is associated with a risk of poor bowel cleansing and leads to a prolonged length of stay and increased costs in these patients. Improvement in bowel preparation quality of hospitalized patients has shown to decrease the length of stay and save more than \$418,200 annually at a tertiary care hospital.

Patient tolerability of the bowel preparation agent may be an important factor affecting the quality of colon cleansing. Large volume (4-liter) polyethylene glycol electrolyte solution (PEG-ELS) bowel preparation is safe and effective, yet poor patient tolerability secondary to the large volume that needs to be ingested remains it's Achilles' heel. Several, small volume (2-liter) bowel preparation agents are available to counteract this problem. Sodium picosulfate, a stimulant laxative, magnesium oxide, and anhydrous citric acid (SP/MC) preparation is a 10-ounce bowel preparation which has demonstrated comparable efficacy, better tolerability and a lower incidence of adverse events than both 2-liter and 4-liter polyethylene glycol based bowel preparations. In addition to the volume related improvement in tolerability and adverse

events with SP/MC versus other FDA approved bowel preparations, strong evidence shows that ingesting at least half of the bowel preparation on the day of the colonoscopy, called split dosing, rather than a single day before dose administered the evening before the examination, not only maximizes the cleansing efficacy but also improves tolerability as well.

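### The survey is tied to the time of drinking, which differs in length and clock timing between arms, so symptoms are compared over different windows

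*Combined protocol and SAP*

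**What the plan says.** The section on patient tolerability and adverse effects gives each patient a survey at enrollment and states: "The patients will be instructed to complete the survey in “real time” (as they are drinking the preparation". The co-investigator or coordinator "will collect the survey from the patient prior to receiving sedation for their colonoscopy procedure" and checks that every question has an answer. The items cover ingestion start and end times (b), amount taken (c), full dose or not (d), symptoms with their type and timing (e), worsening of earlier symptoms (f), ease of use (g), palatability (h) and willingness to use the agent again (i). No common symptom window is set, and no common moment for the ratings.

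The Patient Education section prescribes the intake:

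- Group A drinks 8 ounces "every 10 min the evening before their colonoscopy and finish drinking the bowel preparation in three hours". Group E has the same 3-hour limit and must finish by midnight.
- Group B drinks half "the evening before the colonoscopy and finish drinking the bowel preparation in 1.5 hours", and then: "This dosing scheme will then be repeated 4 hours before the scheduled time of their colonoscopy".
- Group C takes one bottle, then at least five glasses of clear liquid over 5 hours. "The patient will consume the second bottle of SP/MC 5 hours after beginning the first bottle", with at least three more glasses within 2 hours. Group F is similar but must finish by midnight.
- Group D takes the first bottle as in C, and the second 4 hours before colonoscopy: "Patients will consume the second bottle of SP/MC followed by at least 3, 8 ounce glasses of clear liquids over the next two hours".

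Secondary Outcomes lists tolerability first, as a Likert rating. Statistical Analysis models it by proportional odds on preparation and dose type, and names no analysis for symptoms.

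**The concern.** The two factors in the tolerability model, preparation and dose type, also determine when and for how long a patient is told to fill in the survey. A symptom that appears after drinking ends falls outside the instruction as worded. The time after the last day-before intake is therefore covered only if the patient adds entries unprompted, whereas a split-dose patient is told to record again on the day of the procedure. The completeness check does not close this gap, because a sheet fully completed the evening before would pass it.

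The ratings have a related problem. Nothing stops a patient in B or D from rating ease and palatability after the evening portion and never revising the answer. Some split-dose ratings could then describe half a regimen and others the whole of it.

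Tolerability is part of the case for both SP/MC and split dosing, and this survey is the only symptom collection the plan describes.

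**Working it through.** **Check of the protocol's own intake times.**

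- 4 L at 240 ml per 10 minutes: 4000 / 240 × 10 = 167 minutes (2.8 h), consistent with the stated 3 hours.
- One split session: 8 glasses × 10 minutes = 80 minutes (1.3 h), consistent with the stated 1.5 hours.

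**Length and timing of intake by group.** Required SP/MC liquids are counted as drinking; optional extra liquids are not. The documents give no clock times, so the last column assumes a start between 17:00 and 21:00 and colonoscopy between 08:00 and 15:00.

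| Group | Drinking time | End of intake to colonoscopy |
|---|---|---|
| A | 3 h, one session | 8 to 19 h |
| B | 1.5 + 1.5 = 3 h, two days | 4 − 1.5 = 2.5 h |
| C | 5 + up to 2 = about 7 h | 4 to 15 h |
| D | up to 5 + 2 = 7 h, two days | 4 − 2 = 2 h |
| E | within 3 h | at least 8 to 15 h (done by midnight) |
| F | at least 5 h; about 7 h if 2 h is assumed for the last liquids | at least 8 to 15 h (done by midnight) |

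For A, the shortest gap is a 21:00 start ending at 24:00 with colonoscopy at 08:00 (8 h). The longest is a 17:00 start ending at 20:00 with colonoscopy at 15:00 (19 h). For C, the same limits with 7 hours of intake give 4 h and 15 h.

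**Between preparations.** With the required liquids counted, SP/MC runs 5 to 7 hours against 3 for PEG-ELS: 5 / 3 = 1.7 and 7 / 3 = 2.3 times as long. If only the bottles count, the order presumably reverses. The Introduction says the SP/MC "preparation is a 10-ounce bowel preparation which has demonstrated comparable efficacy, better tolerability and a lower incidence of adverse events", but no drinking time per bottle is stated, so no ratio can be computed.

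**Between dose types.** A and B have the same total drinking time (3 h against 3 h). The difference is in the clock: B's second session starts 4 hours before colonoscopy, while A has finished the evening before. Elapsed time from first to last intake is 8.5 to 19.5 h in B and 9 to 20 h in D on the assumed times, against 3 h in A and about 7 h in C.

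**A common window.** From first intake to colonoscopy is 11 to 22 h on the same assumptions, and it is identical across arms for the same start and procedure times. It is not perfectly equal in practice, because A and B start in the evening and the other groups may start in the afternoon. For a 10:00 colonoscopy, a 15:00 start gives 19 h and a 19:00 start gives 15 h.

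**Required liquids.** (5 + 3) × 8 ounces = 64 ounces, or 8 × 240 ml = 1920 ml. Item g does not say whether this volume is part of what is rated.

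**The case against.** The strongest reply is that the instruction asks for prompt entry and sets no cut-off. Items b, c, d and i cannot sensibly be answered until drinking is over, item e asks for symptom timing without limit, and the sheet stays with the patient until shortly before sedation. This stands in part: late symptoms can be entered. But nothing tells the patient to do so or staff to ask, so capture depends on individual initiative.

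Second, the planned endpoint is a Likert rating and not a count over time, and the length of a regimen is properly part of what a patient rates. This also stands, and it is why the point weighs more on symptoms, which have no planned model. It does not answer the possibility of rating a split regimen halfway through.

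Three stronger readings are tempting and are not supported:

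- **That the wording favours SP/MC.** This needs the bottle-only reading. Counting the required liquids makes SP/MC's window the longer one. Nor do the documents describe when symptoms appear after SP/MC.
- **That the periods differ several-fold by design.** With required liquids counted, drinking time differs 1.7- to 2.3-fold between preparations and not at all between A and B. Larger ratios need an unstated bottle time or assumed clock times.
- **That every rating should be made just before sedation.** B and D would then rate about 2 to 2.5 hours after intake, but A 8 to 19 hours and C 4 to 15 hours after it on the assumed times. That exchanges one difference between arms for another.

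**Conclusion.** The point holds as a gap in the survey instruction. The plan fixes neither a common symptom window nor a common stage for the ratings, and its wording, read literally, gives the arms windows of different length and clock timing. Symptom comparisons between preparations and between single and split dosing are exposed to this; the Likert endpoint is exposed less.

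The direction of any bias is open and its size cannot be derived from the documents. The conclusion rests on the literal reading of the instruction. The differences in timing follow from the prescribed regimens; the hour ranges that depend on time of day rest on the assumed clock times. Neither the primary endpoint nor the sample size is affected. This is a worthwhile, inexpensive improvement, and the trial does not depend on it.

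**What to change.** In the section on tolerability and adverse effects:

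1. Keep real-time entry, but state that items e and f cover first intake until survey collection before sedation, in all six groups.
2. Have the person collecting the survey ask about symptoms since the last entry.
3. Record start and end times for each intake session, so that the length of each patient's window can be reported.
4. Have items g, h and i answered once, after the last portion of the assigned regimen (or when the patient stops, if it is not finished).
5. Word item g as ease of completing the whole assigned regimen, including the required clear liquids.

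The cost is a slightly longer survey and a brief question at a contact that already takes place. Some recall remains for symptoms in the day-before groups, limited by the retained real-time entries. The clock time of the ratings will still differ between arms, but each rating will describe a regimen whose intake has ended.

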### **SAMPLE SIZE CALCULATION:**

Preliminary data has been gathered over the last one year at Cleveland Clinic which has shown adequate bowel preparation rates (as defined by the reported preparation quality of good or excellent on the Aronchik scale) in about 46 % of all hospitalized patients undergoing colonoscopy. Due to the educational initiative currently underway at our institution, we will assume that the rates of adequate bowel preparation will be 50 % (which will be taken as the rate of adequate preparation in our control arm of the 4 L PEG-ELS). To demonstrate a 10 % increase in rates of adequate cleansing with the use of P/MC at a confidence level of 95% and a power of 85 %, a sample size of at least 886 subjects would be required. Counteracting for a possible difference that may exist between our estimated and existing rates of satisfactory bowel preparation, we will increase the sample size by at least 10 % for a total of 1000 patients (250 patients per group).

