### **METHODOLOGY:**

#### **STUDY DESIGN:**

A randomized, single-center, assessor-blinded trial will be conducted at Cleveland Clinic, a tertiary healthcare center in Ohio, United States. Eligible inpatients at the Cleveland Clinic scheduled for colonoscopy under conscious sedation or general anesthesia will be invited to participate.

Patients eligible for conscious sedation will be randomized at a 1:1:1:1 ratio to receive 1 of the 4 proposed bowel preparation regimens using block randomization. This will be done with a computer-aided system prior to study commencement. The four groups are as follows:

- Group A: 4 Liter PEG-ELS administered as a single day before dose the evening before the colonoscopy,
- Group B: 4 Liter PEG-ELS administered as a split dose the evening before and 4 hours prior to the colonoscopy (currently the standard to which other bowel regimens are compared),
- Group C: SP/MC administered as a single day before dose the afternoon or early evening before the colonoscopy,
- Group D: SP/MC administered as a split dose the afternoon or early evening day before and 4 hours prior to the colonoscopy.

Patients who require general anesthesia will be randomized at a 1:1 ratio to the single, ‘day before dose’ only groups for both PEG-ELS and SP/MC since the anesthesia protocol at our institution mandates strict enforcement of nothing per oral after midnight on the day of the procedure.

- Group E: 4 Liter PEG-ELS administered as a single day before dose the afternoon or early evening before the colonoscopy,
- Group F: SP/MC administered as a single day before dose the afternoon or early evening before the colonoscopy,

- All procedures will be done at the endoscopy suite on the main campus at Cleveland Clinic by a board certified gastroenterologist. The physician and the patients will not be blinded due to major differences in the volume and timing of the bowel cleansing regimens. Primary end-points of this study will be measured between the participants in the all 6groups.

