### **FEASIBILITY:**

A total of 1145 inpatient colonoscopies were done at Cleveland Clinic from April 2018 to April 2019, averaging 190 colonoscopies per month. Assuming a recruitment rate of 75 %, 12 months of recruitment will be needed to obtain a sample size of 1000 patients (250 per group) and complete our study.

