#### **STATISTICAL ANALYSIS:**

Descriptive data will be presented for all 4 groups; these include means  $\pm$  standard deviations, median [25th, 75th percentiles] or frequency (percent). Regression analysis will be used to assess the primary and secondary outcomes of interest; logistic regression will be used to model satisfactory bowel preparation and need of repeat procedure while proportional odds logistic regression will be used to model tolerability. For each model, the outcome of interest will be modeled as the dependent variable with the type of bowel preparation (PEG-ELS vs. SP/MC) and type of dose (single vs. split) as the independent variables; the interaction between these two will be tested and included in the models if  $p < 0.10$ . SAS (version 9.4, The SAS Institute, Cary, NC) will be used for all analyses and a  $p < 0.05$  will be considered statistically significant.

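### The planned 1000 patients at 250 per group fit four groups, but six are randomized, and the plan does not say how the general-anesthesia groups count towards sample size or enter the dose analysis

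*Combined protocol and SAP*

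**What the plan says.** Under Study Design, patients eligible for conscious sedation are "randomized at a 1:1:1:1 ratio to receive 1 of the 4 proposed bowel preparation regimens" (A-D: two agents, each as a single or a split dose). A second allocation follows: "Patients who require general anesthesia will be randomized at a 1:1 ratio to the single" day-before groups, E and F, one per agent. The section closes with "Primary end-points of this study will be measured between the participants in the all 6groups".

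The Sample Size Calculation section sizes one contrast: "To demonstrate a 10 % increase in rates of adequate cleansing with the use of P/MC", from 50%, at 95% confidence and 85% power, which needs 886 patients. It then adds a margin: "we will increase the sample size by at least 10 % for a total of 1000 patients (250 patients per group". Feasibility repeats the figure: "12 months of recruitment will be needed to obtain a sample size of 1000 patients (250 per group) and complete our study".

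Statistical Analysis says "Descriptive data will be presented for all 4 groups" and fits logistic models with agent and "type of dose (single vs. split) as the independent variables". An agent-by-dose interaction is kept if its p-value is below 0.10. No sedation term is listed. The Hypothesis section states two expectations for adequate cleansing: one for agent, one for split against single dosing.

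**The concern.** No section reconciles the four groups of the sample size with the six of the design. The size of E and F, the expected share of general-anesthesia patients, and whether E-F fall inside the 1000 are all unstated.

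Two things are at stake. The first is what the stated size delivers: a reader cannot tell how many patients stand behind either hypothesis. The second is validity. General-anesthesia patients could never be assigned a split dose, so if they are analysed with the rest, all of them fall on the single-dose side. The listed model has nothing to separate that from a dose effect.

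**Working it through.** **Inputs from the plan.** Control rate 50%; 10-point gain with SP/MC; alpha 0.05 (taken as two-sided, which reproduces the plan's figure); power 85%; 886 raised to 1000; 250 per group; allocation 1:1:1:1 in A-D and 1:1 in E-F.

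**Assumptions, not in the plan.** The general-anesthesia share g, shown from 10% to 50%; a dose effect of 50% vs 60%; a sedation-type difference of 10 points.

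**1. The plan's figure.** With pooled variance under the null, n per arm = [1.96·√(2·0.55·0.45) + 1.036·√(0.50·0.50 + 0.60·0.40)]² / 0.10² = (1.379 + 0.725)² / 0.01 = 442.9. Rounded up, that is 443 per arm and 886 in total, as stated. Power at 500 vs 500 is Φ[(0.10·√500 − 1.379)/0.70] = Φ(1.224) = 89.0%.

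**2. Group counts.** 1000/250 = 4, against six groups.

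- *1000 is the study total:* A-D hold 1000(1−g)/4 = 250(1−g) each, and E-F hold 500g each.
- *1000 is A-D only:* the study total is 1000/(1−g), and E-F are extra.
- *A group means one of four regimens (A+E, B, C+F, D):* A and B are equal by design, so A+E exceeds B. At g = 20% with 1000 in total, the four hold 300, 200, 300 and 200.

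**3. Results over g.** Power is for 50% vs 60% and uses the formula in step 1. The second to fourth columns take 1000 as the total.

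| g | Each of A-D | Each of E-F | Power at 500(1−g) per arm | Study total if A-D = 1000 | General-anesthesia share of the single-dose arm |
|---|---|---|---|---|---|
| 10% | 225 | 50 | 85.6% | 1111 | 18% |
| 20% | 200 | 100 | 81.3% | 1250 | 33% |
| 30% | 175 | 150 | 75.9% | 1429 | 46% |
| 40% | 150 | 200 | 69.3% | 1667 | 57% |
| 50% | 125 | 250 | 61.4% | 2000 | 67% |

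The power column applies to split vs single within A-D. It applies equally to agent if E-F are left out. With 1000 as the total, A-D fall below 886 once g exceeds 1 − 886/1000 = 11.4%.

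**4. Agent comparison, with 1000 as the total.** Agent is allocated 1:1 in both randomizations, so pooling all six groups gives 500 vs 500 and 89.0% for the main effect. This needs E-F in the model and no interaction term. Without E-F, agent has 500(1−g) per arm: 400 vs 400 and 81.3% at g = 20%. With the interaction kept, the agent effect under split dosing rests on B vs D: 200 vs 200 at g = 20%, giving Φ[(0.10·√200 − 1.379)/0.70] = Φ(0.050) = 52%.

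**5. Dose comparison if E-F enter.** The general-anesthesia share of the single-dose arm is 1000g/[500(1−g) + 1000g] = 2g/(1+g). It depends only on g, so it is the same whichever way the 1000 is read. At g = 20% it is 200/600 = 33%. If the satisfactory-cleansing rate on single dose differs by 10 points between sedation types, the crude split-minus-single difference shifts by 0.333 × 10 = 3.3 points with no change in the true dose effect. The shift flatters split dosing if general-anesthesia patients do worse, and masks its benefit if they do better.

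**The case against.** The strongest reply is that the plan claims no power for dose. Its 85% is tied to agent, 886 is right, and 4 × 250 = 1000 is right. Powering one of two hypotheses is a legitimate choice. All of this stands, so this is an inconsistency between sections, not an arithmetic error.

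A reader might infer that the split-versus-single hypothesis is underpowered. The documents do not support that. They give neither g nor a dose effect. If 1000 means A-D only, dose keeps 500 vs 500. If 1000 is the total, an assumed 50% vs 65% still has 92.6% power at g = 50%. The power column in the working is illustration.

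A reader might also infer that six groups at 250 require 1500 patients. That does not follow either: the calculation sizes a two-arm agent contrast, not each group.

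In the plan's favour, "Descriptive data will be presented for all 4 groups" may mean four regimens, and E-F may be meant to stay out of the models. Either is possible, but neither is written, and the regimen reading still does not give 250 each. The opposite comfort, that agent keeps 89% power whatever g is, holds only under the conditions in step 4.

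**Conclusion.** The inconsistency is certain and needs no assumed figure beyond some patients requiring general anesthesia, which the design presupposes. Either 250 per group is not delivered, or E and F are unsized and the study exceeds 1000.

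The stated power is correct for the agent main effect. With 1000 as the total, the 89% at 500 vs 500 depends on E-F being included and the interaction being absent.

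The more serious part is the undefined analysis set for dose. Fitting the listed model to all six groups would confound dose with sedation type. How large that bias would be rests on two unstated quantities, g and the sedation-type difference; the 3.3 points show its scale and do not predict it. The point should be corrected before analysis. It does not show that the trial is too small.

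**What to change.** 1. In Sample Size Calculation and Feasibility, state whether 1000 covers all six groups or A-D only. Replace the per-group figure with expected sizes for A-D and for E-F, based on the site's sedation mix.
2. In Statistical Analysis, align the number of groups with Study Design (six groups, or four regimens if that is meant) and say which groups enter each model.
3. Estimate split vs single from A-D only, or from a six-group model with a sedation term. If the agent-by-dose interaction is kept in the six-group model, add agent-by-sedation as well, so that dose is still identified within A-D. Estimate the agent effect over all six groups, with sedation type as a stratum or covariate.
4. State that the 85% applies to the agent main effect only. Any dose power can be given over a range of assumptions and labelled as illustration.

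The cost is text in three sections plus one planning figure, the expected general-anesthesia share, which the sponsor must supply. Sedation type is already among the Variables to be Studied, so no new patient data are needed. The downside is that E-F add nothing to the dose comparison and the stated group sizes become less favourable. If 1000 turns out to mean A-D only, the stated total rises because it was incomplete; the fix itself asks for no added enrolment.
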